### **16.3.3. Primary Endpoint Analysis**

The primary endpoint (change of TSQM-9 convenience domain at week 12) will be analysed by a repeated measures analysis of variance adjusted for baseline factors (age, sex, disease duration, previous treatment duration, EDSS).

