### **16.3.2. General Methods of Analysis**

The primary and secondary endpoints will be evaluated using a repeated measures ANOVA. The repeated measures ANOVA is used to compare group means on a dependent variable across repeated measurements of time. This statistical method is used for making simultaneous comparisons between two or more means of two or more related, not independent, groups.

However, in addition, it could be useful to apply a general linear mixed model that models for group means as fixed effects while simultaneously modeling for individual subject variables as random effects (12).

This kind of model is a subject-specific model and is a choice for analysing longitudinal data.

Unlike the repeated measures ANOVA, which requires a complete balanced array of data, the mixed model can accommodate a dataset with a large portion missing. Although the repeated measures ANOVA requires a fixed time schedule among all individual units, the mixed model can accommodate flexible time schedules. Furthermore, rather than treating time as a categorical variable, as in the repeated measures ANOVA, the mixed model is capable of treating time as either a continuous variable or a categorical variable or both.

Spearman's correlation coefficient measures the strength of association between two ranked variables.

Differences will be considered statistically significant if the p-value will be less or equal to a type I error =0.05 (two-sided test).

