### **16.5. Sample Size Considerations**

Data for estimating the sample size were derived from studies reporting the distribution (mean value and standard deviation) of the TSQM-9 in MS patients treated with IFN (9). Assuming an average value of the overall convenience domain at baseline of 55 (SD=16) (9), with 250 subjects we have a power of 90% to detect a change of 3 points on the overall convenience domain (from 55 to 58) under the conservative hypothesis of a SD=16 (9) for the difference between baseline and week 12. However, by assuming a drop-out rate up to 10% during the study, we consider it appropriate to enrol a total of 275 patients.

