In addition, routine clinical assessments will be performed in order to check the safety of the Peg-IFN ongoing treatment.

Laboratory Safety Assessments

At the Investigator's discretion, the following routine laboratory tests can be carried out, in order to monitor the safety profile of the ongoing treatment based on Peg-IFN:

- Hematology: RBC- WBC –Haemoglobin- Haematocrit- MCV- MCH – MCHC - Platelets Count – Lymphocytes- Monocytes – Neutrophils – Eosinophils – Basophils
- Blood chemistry: creatinine, blood urea nitrogen (BUN), alkaline phosphatase, ALT, AST, gamma-glutamyl-transferase (GGT).

A pregnancy hCG test (blood sample) will be performed at the baseline visit (T0) to exclude pregnancy, if applicable (it is not required if the subject is post-menopausal or surgically sterilized).

9. Missing data

For missing data in TSQM-9, MSTCQ and MusiQoI see paragraph Variable of analysis.

For the other variables no imputation technique will be apply.

10. Statistical analysis

The primary and secondary endpoints will be evaluated using a repeated measures ANOVA. The repeated measures ANOVA is used to compare group means on a dependent variable across repeated measurements of time. This statistical method is used for making simultaneous comparisons between two or more means of two or more related, not independent, groups.

However, in addition, it could be useful to apply a general linear mixed model that models for group means as fixed effects while simultaneously modeling for individual subject variables as random effects (12). This kind of model is a subject-specific model and is a choice for analysing longitudinal data. Unlike the repeated measures ANOVA, which requires a complete balanced array of data, the mixed model can accommodate a dataset with a large portion missing. Although the repeated measures ANOVA requires a fixed time schedule among all individual units, the mixed model can accommodate flexible time schedules. Furthermore, rather than treating time as a categorical variable, as in the repeated measures ANOVA, the mixed model is capable of treating time as either a continuous variable or a categorical variable or both.

Spearman's correlation coefficient measures the strength of association between two ranked variables.

Differences will be considered statistically significant if the p-value will be less or equal to a type I error =0.05 (two-sided test).

11. Efficacy data

a. Primary Endpoint Analysis

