The primary endpoint is to evaluate the changes from baseline in the score of convenience satisfaction domain of TSQM-9 at 12 weeks. (*Stata instruction: anova var1 time, repeated(time)*)

b. Secondary Endpoints Analysis

- Changes from baseline in the score of all domains of TSQM-9 at 24 weeks;
- Changes from baseline in patient adherence to study treatment survey at 12 and 24 weeks;
- Changes from baseline in the score of FSS (Fatigue Status Scale) at 12 and 24 weeks;
- Changes from baseline in the score of Adapted Sclerosis Treatment Concerns Questionnaire (MSTCQ) at 12 and 24 weeks;
- Changes from baseline in the score of Multiple Sclerosis International Quality of Life questionnaire (MusiQoL) at 12 and 24 weeks;
- Changes from baseline in clinical measures (ARR, percentage of relapse-free patients), measures at 24 weeks.

All the above primary and secondary endpoints will be analysed by a repeated measures analysis of variance adjusted for baseline factors (age, sex, disease duration, previous treatment duration, EDSS) (*Stata instruction: anova var1 var2 time, repeated(time)*).

Correlations between variables will be assessed by a Spearman rank correlation coefficient (*Stata instruction: spearman var1 var2*).

[figure not shown]
To evaluate the relationship between patients' satisfaction and social-demographic factors (age, sex, employment working, level of education, etc.) and clinical characteristics (ARR, disability, etc.) generalized linear mixed models for repeated measurements will be performed (*Stata instruction: mixed var1 var2 || patient:*).

12. Safety Data

a. Adverse events

All events will be coded using the Medical Dictionary for Regulatory Activities (MedDRA). Type and incidence of all AEs will be tabulated. Severity and drug relatedness of all reported AEs will be tabulated.

b. Clinical Laboratory Tests

	Statistical Analysis Plan Protocol N. BIIT0215– Platinum	Pag. 14 di 18
---	---	---------------

For the clinical laboratory data, descriptive statistics will be generated for all tests performed. Laboratory abnormalities will be determined in accordance with the normal ranges of the clinical laboratory. Laboratory abnormalities will be tabulated.

13. Tables

The following tables will be repeated for each visit, if applicable.

- P1. Number and percentage of patients enrolled per center
- P2. Number and percentage of patients stratified by gender; mean and median age, range and interquartile range;

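### SAP section 11 does not define one valid primary analysis of the week-12 convenience change: it gives two unranked commands, neither with a patient term, and the covariate terms leave the mean change as it was

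*Protocol*

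**What the plan says.** Protocol 16.3.3 names one primary analysis. Of the week-12 change in the convenience score it says that this "will be analysed by a repeated measures analysis of variance adjusted for baseline factors (age, sex, disease duration, previous treatment duration, EDSS"). It does not say whether the five factors enter as main effects or as interactions with time. The synopsis repeats the statement.

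SAP section 11.a attaches an unadjusted command to the primary endpoint: "Stata instruction: anova var1 time, repeated(time"). Section 11.b then states: "All the above primary and secondary endpoints will be analysed by a repeated measures analysis of variance adjusted for baseline factors", and its command adds a single generic covariate, `var2`, as a main effect. Neither command has a patient term or a covariate-by-time term. No ranking of the two is given.

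The table list follows the same split. P18 reports the change in convenience at 12 weeks. P20 reports the adjusted analysis of variance for the change at 12 and 24 weeks. On missing data, SAP section 9 refers the questionnaires to their scoring rules and then says: "For the other variables no imputation technique will be apply".

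**The concern.** The primary question is whether the mean within-patient change differs from zero. A valid test compares each patient with himself or herself, and the plan must say which single result answers the question. Here the outcome variable (score or change), the error term and the form of the covariates are all open, and two commands compete.

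Age, sex, disease duration, previous treatment duration and EDSS are recorded at baseline and are constant within a patient. As main effects in a model of the score they describe differences in level between patients. They do not describe who changes. The report could therefore present a result as adjusted for baseline factors when the change has not been adjusted, or present a p-value from an error term that ignores the pairing. It could also lose patients for covariates that do not alter the estimate.

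**Working it through.** **Inputs.** From protocol 16.5: "with 250 subjects we have a power of 90% to detect a change of 3 points", a baseline value for the "overall convenience domain at baseline of 55 (SD=16) (9"), and SD 16 for the change ("under the conservative hypothesis of a SD=16 (9) for the difference between baseline and week 12"). From protocol 16.3.2: significance at "less or equal to a type I error =0.05 (two-sided test"). All power figures use the normal approximation unless stated.

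**1. The plan's own figure.** Paired SE = 16/√250 = 1.012. Power = Φ(3/1.012 − 1.960) = Φ(1.005) = 84.3% (noncentral t: 84.0%). A power of 90% would need (16 × (1.960 + 1.282)/3)² ≈ 299 patients. The stated 90% is not reproduced two-sided; a one-sided 0.05 test gives 90.7%. That mismatch is a separate matter. Here 84.3% serves only as the benchmark for a paired test.

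**2. Commands read literally, with no patient term.** The two visits are then treated as independent groups. The documents give no SD at week 12; assume 16 at both visits, which with an SD of change of 16 implies a correlation of 1 − 256/(2 × 256) = 0.5.
- SE = 16 × √(2/250) = 1.431. Power = Φ(3/1.431 − 1.960) = 55.4%.
- If the covariates explain an assumed 10%, 20% or 30% of the score variance, SE = 1.431 × √(1 − R²) = 1.358, 1.280, 1.197, and power = 59.9%, 64.9%, 70.7%.
- The loss depends on the assumed visit SD. Holding the SD of change at 16, a visit SD of 14 gives SE 14 × √(2/250) = 1.252 and unadjusted power 66.9%; a visit SD of 12 gives SE 1.073 and 79.8%.

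So under this reading the adjusted and unadjusted p-values differ even with complete data. In one simulated set of 250 patients and two visits, the time F was 1.42 without the covariates and 1.84 with them, for the same estimated change.

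**3. Score as outcome, with a patient term.** A factor constant within a patient is a linear combination of the patient indicators, so adding it as a main effect changes nothing in the within-patient comparison. Simulation confirms this: with two visits F = 2.939237 on 249 error df with and without the five factors; with three visits F = 18.376990 on 498 df both ways. The equality also held when the factors were made to influence the change.

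**4. Change as outcome.** Main effects then do act on the change. At average covariates the estimated mean change stayed the same; its SE went from 1.130 to 1.044 when the factors predicted change, and from 0.990 to 0.999 when they did not. Two difficulties remain. With week 12 alone there is one change per patient and nothing is repeated. With weeks 12 and 24 together, as P20 is worded, a time factor compares the two changes with each other, not the week-12 change with zero.

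**5. Missing covariates.** The rate is not in the documents. Assume 4% to 10% of patients lack at least one factor: n = 250 × 0.96 = 240 or 250 × 0.90 = 225. Paired power = Φ(3√240/16 − 1.960) = 82.8% or Φ(3√225/16 − 1.960) = 80.3% (noncentral t: 82.5% and 80.0%), against 84.3%.

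**The case against.** The SAP commands are plainly templates: one `var2` stands for five factors, so the missing patient term may be shorthand and not a decision. That is fair. The 55% is what the written command would give under the assumed visit SDs; it is not a forecast of what the analyst will run. But nothing else in SAP section 11 supplies the error term for this analysis.

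A reader might infer that the adjustment does nothing at all. The documents do not support that. It is exact only for the score as outcome, a patient term and complete data, and neither the outcome nor the patient term is settled. Without a patient term the covariates change the error and the p-value. With change as the outcome, which is how protocol 16.3.3 and P20 are worded, they affect precision. What holds across the readings, with complete data, is that the mean change at average covariates does not move.

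A reader might also infer that two primary analyses were declared so that one could be picked. The protocol names only the adjusted one, and P18 is worded as a description, not as a test. What stands is that the SAP adds an unadjusted command without ranking it.

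The covariate loss is assumed and modest. Disease duration and previous treatments are scheduled baseline items, so the loss could be nearly zero. Finally, keeping an adjusted primary model would also be defensible if its outcome, patient term and covariate form were fully specified. Preferring the unadjusted paired change is a choice, made because it is simple and keeps every patient with both scores.

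**Conclusion.** The point holds as a defect of specification with a real statistical consequence. SAP section 11 gives two unranked commands for the primary endpoint, and neither, as written, is a paired analysis. Taken literally, power falls from about 84% to about 55% unadjusted, or 60-71% with covariates at assumed R² of 0.1-0.3. These figures rest on n=250, a change of 3, SD of change 16 and an assumed SD of 16 at both visits; the loss is smaller if the visit SDs are smaller. If the pairing is restored and the score is modelled, covariate main effects leave the estimate, SE and p-value untouched, so the label "adjusted" would be wrong. The cost of missing covariates, about 2 to 4 power points at an assumed 4-10% loss, is secondary. Whether the change depends on these factors is not tested by a main-effects model of the score. The plan should be corrected before analysis.

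**What to change.** In protocol 16.3.3 (with the matching synopsis text) and SAP section 11, make the paired mean change from T0 to T1 in the convenience score, with its 95% CI, in FAS patients with both scores, the single primary analysis. Report it in P18.

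In P20, replace the main-effects model with a supportive regression of the change on mean-centred age, disease duration, previous treatment duration and EDSS, all entered as continuous, plus sex. Run it separately for week 12 and week 24. A model of the score with a patient term and factor-by-time terms is an equivalent route. State how many patients are left out for a missing factor.

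Make the same correction to the secondary models of the same form: P26 (MSTCQ), P29 (MusiQoL) and P32 (FSS).

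The cost is protocol and SAP wording and a few lines of code, with no new data. The small downside is that the protocol's prespecified adjusted analysis becomes supportive.

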#### **16.3.4. Secondary Endpoints Analysis**

All the other endpoints will be analysed according to the same technique. Correlations between variables will be assessed by a Spearman rank correlation coefficient.

To evaluate the relationship between patients' satisfaction and social-demographic factors (age, sex, employment working, level of education, etc.) and clinical characteristics (ARR, disability, etc.) generalized linear mixed models for repeated measurements will be performed.

### **16.4. Safety Data**

#### **16.4.1. Analysis Population**

Safety population = All Patients Treated Set (APTS), consisting of all enrolled patients who took at least one dose of study medication;

#### **16.4.2. Methods of Analysis**

Adverse events

All events will be coded using the Medical Dictionary for Regulatory Activities (MedDRA). Type and incidence of all AEs will be tabulated. Severity and drug relatedness of all reported AEs will be tabulated.

Clinical Laboratory Tests

For the clinical laboratory data, descriptive statistics will be generated for all tests performed. Laboratory abnormalities will be determined in accordance with the normal ranges of the clinical laboratory. Laboratory abnormalities will be tabulated.

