**Study Population:**

This study will be conducted in subjects with Relapsing-Remitting Multiple Sclerosis (RRMS) as per 2010 McDonald criteria, with EDSS between 0.0 and 5.0 and unsatisfied with the current injectable subcutaneous Interferons.

Detailed criteria are described in the protocol.

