## 4.2. Schedule of Events

Tests and assessment	T0 (Enrollment)	T1 (12 weeks) ± 1 week	T2 (24 weeks) ± 1 week	ET Early termination
Inclusion/Exclusion criteria	X			
Informed consent	X			
Social-demographics (e.g., age, gender)	X			
Medical history (e.g., disease duration, previous disease history and treatments)	X			
On-treatment medical information (e.g., concomitant therapies, comorbidities)	X	X	X	X
Pregnancy hCG test	X			
Clinical and neurological evaluation (including recording of relapses and EDSS)	X	X	X	X
Drug Supply	X	X		
Assessment of patients' satisfaction (TSQM-9)	X	X	X	X
Assessment of patients' adherence	X	X	X	X
Assessment of patients' injection-system satisfaction (Adapted MSTCQ)	X	X	X	X
Assessment of patients' HRQoL (MusiqoL)	X	X	X	X
Assessment of patients' fatigue (FSS)	X	X	X	X
Routine Laboratory tests	X	X	X	X
Adverse events, pregnancy exposure, episodes of overdose		X	X	X
Drug Accountability 		X	X	X

1. If a dose is missed, it should be administered as soon as possible, within 7 days.

CONFIDENTIAL

The information contained herein may not be used, disclosed, or published without the written consent of Biogen Italia

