## **7. STUDY DESIGN**

### **7.1. Study Overview**

This is a 6 month, phase IV, open-label, single-arm, interventional, multicentric study, based on self-administered questionnaires (as described in Methods) and aimed at evaluating patient-reported effects on user's satisfaction of Peg-IFN beta-1a therapy on patients unsatisfied with other injectable, subcutaneous Interferons. The relevant evaluations will be performed at baseline, week 12 and week 24.

Informed consent will be obtained at baseline prior to study enrolment and before collection of all relevant clinical information (i.e., relapses, EDSS).

Clinical evaluation and questionnaire administration will be performed at baseline (within 2 weeks before Peg-IFN beta-1a therapy onset) and after 12 and 24 weeks.

Subjects may elect to discontinue from study treatment at any time, due to medical reasons (contraindications, medical conditions that necessitate drug discontinuation according to the Investigator) or at personal and/or Investigator's discretion. In all cases, reasons for discontinuation from investigational treatment or withdrawal from the study will be recorded in the subject's CRF.

All relevant and required information about any adverse event (serious and non-serious), including laboratory abnormalities and about pregnancy and cases of overdose occurring during the study will be collected and registered in the subject's CRF.

In case of SAE, pregnancy, or cases of overdose, the Investigator will have to notify Biogen Italia Srl's Drug Safety Unit immediately and no later than 24 hours from its occurrence, by fax or e-mail. Any event follow-up will have to be notified to Biogen Italia's Drug Safety Unit within 24 hours from its recording.

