## **8. STUDY POPULATION**

### **8.1. Inclusion Criteria**

To be eligible to participate in this study, candidates must meet the following eligibility criteria at Baseline (T0):

1. Ability to understand the purpose and risks of the study and provide signed and dated informed consent and authorization to use protected health information (PHI) in accordance with national and local subject privacy regulations.
2. Aged between 18 and 65 years old inclusive, at the time of informed consent.
3. Subjects diagnosed with Relapsing Remitting MS according to 2010 McDonald criteria.
4. Subjects with EDSS score between 0.0 and 5.0 at baseline.
5. Treatment with injectable subcutaneous Interferons with score < 58 in the “convenience satisfaction” domain of TSQM-9.
6. Period of stability from last relapse of at least 30 days before the baseline visit.
7. Treatment with intravenous corticosteroids completed at least 30 days before the baseline visit (assumption of oral cortisone allowed as long as within 4 mg per day for no longer than 3 days).

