P21. Number and percentage of patient who have correctly taken the prescribed doses of treatment within the last 28 days; if don't, mean and median, interquartile range and range of injections have not been performed during the last 28 days;

P22. Number and percentage of patients per reasons to non correctly taken the treatment:

- a) Anxiety for injection
- b) Skin reaction
- c) Forgot to take the dose
- d) Pain at the injection site

- e) Depression
- f) Headhache
- g) Fatigue
- h) Flu-like symptoms
- i) “I did not want to”
- j) “I am not sure of the benefits”
- k) “I am tired of injections”
- l) No one available for injection
- m) Uncomfortable dosing
- n) “I am pregnant / I have planned a pregnancy”
- o) Other

- P23. Mean and median, interquartile range and range of injections expected from the therapy taken in the last 28 days;
- P24. Mean and median, interquartile range and range of MSTCQ;
- P25. Change from baseline in the score of the MSTCQ at 12 and 24 weeks;
- P26. Adjusted repeated measures analysis of variance for change of the MSTCQ at 12 and 24 weeks;
- P27. Mean and median, interquartile range and range of MusiQol;
- P28. Change from baseline in the score of the MusiQol at 12 and 24 weeks;
- P29. Adjusted repeated measures analysis of variance for change of the MusiQol at 12 and 24 weeks;
- P30. Mean and median, interquartile range and range of FSS;
- P31. Change from baseline in the score of the FSS at 12 and 24 weeks;
- P32. Adjusted repeated measures analysis of variance for change of the FSS at 12 and 24 weeks;
- P33. Mean and median, interquartile range and range of EDSS;
- P34. Change from baseline in the score of the EDSS at 12 and 24 weeks;
- P35. ARR, Annualized Relapse Rate
- P36. Number and percentage of abnormalities in laboratory values per each test;
- P37. List of all laboratory abnormalities;
- P38. Number and percentage of adverse events stratified by severity;

	
Statistical Analysis Plan Protocol N. BIIT0215– Platinum
	
Pag. 18 di 18

--	---	---

- P39. List of all adverse events with related characteristics;
- P40. Number and percentage of patients who discontinued the study and reasons of discontinuity;
- P41. Number and percentage of patients who experienced pregnancy during the study and outcome of pregnancy.

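### Patients switch from another interferon, but no planned laboratory summary separates abnormalities that are new or worse since T0 from those already present

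*Protocol*

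**What the plan says.** Entry criterion 5 (Protocol 8.1) requires "Treatment with injectable subcutaneous Interferons with score < 58" on the convenience domain, and the synopsis describes the population as "unsatisfied with the current injectable subcutaneous Interferons". Protocol 7.1 places the baseline evaluation within two weeks before the first Peg-IFN dose. No washout is described. Sections 8.1 and 8.2 name no laboratory limits for entry; the only indirect route is the exclusion for contraindications in the product label.

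Laboratory abnormalities are a secondary endpoint (Protocol 6.2.2 and 16.1.2). For their analysis, Protocol 16.4.2 states "For the clinical laboratory data, descriptive statistics will be generated for all tests performed" and then "Laboratory abnormalities will be determined in accordance with the normal ranges of the clinical laboratory". SAP 12.b has the same text. SAP section 13 plans P36, "Number and percentage of abnormalities in laboratory values per each test", and P37, a listing of all laboratory abnormalities. The section opens with "The following tables will be repeated for each visit, if applicable", so T0, T1 and T2 each get their own count.

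On timing, the Schedule of Events (Protocol 4.2) marks "Routine Laboratory tests" at T0, T1, T2 and early termination. Protocol 14.2 and the matching SAP text leave the same tests to the investigator's discretion.

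**The concern.** In a switch study the T0 sample is not an untreated baseline. Protocol 15.3.3 lists liver and blood problems among the known effects of Peg-IFN, and the planned panel covers transaminases, GGT, lymphocytes and platelets. Some patients may already be out of range at T0 on the previous interferon. A patient with the same out-of-range result at every visit is counted at every visit, and a patient who becomes abnormal for the first time at T1 adds to the same T1 total.

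The most useful laboratory question here is how many patients developed, kept, lost or worsened an abnormality after the switch. A set of visit-by-visit percentages does not answer it. Similar percentages at T0 and T1 could mean that nothing changed, or that new abnormalities were offset by others that resolved. P36 also counts abnormalities rather than patients, unlike P40 and P41, and gives no denominator. With discretionary testing, the denominator may differ between visits.

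**Working it through.** The documents give no laboratory abnormality rate, so there is no planned figure to reproduce. The check asks what P36 can and cannot determine. Every rate below is an assumption; only the 275 planned patients come from the documents.

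**Step 1: what two visit-wise percentages determine.** Let p0 and p1 be the shares abnormal at T0 and T1 on one test, with the same patients tested at both visits. The share normal at T0 and abnormal at T1 must lie between max(0, p1 − p0) and min(p1, 1 − p0). With equal shares the lower limit is 0 and, at the rates used here, the upper limit is p1.

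| Abnormal at T0 and at T1 (assumed) | Fewest new | Most new, N = 275 |
|---|---|---|
| 5% and 5% | 0 | 0.05 × 275 = 13.75, about 14 |
| 10% and 10% | 0 | 0.10 × 275 = 27.5, about 28 |
| 20% and 20% | 0 | 0.20 × 275 = 55 |

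In the 10% row, 0 means that every T0 abnormality persisted and none arose. About 28 means that every T0 abnormality resolved and as many new ones replaced them. P36 would show the same percentages in both cases.

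**Step 2: how much of the T1 count could be carried over.** Let s be the share of T0 abnormalities that persist and q the onset rate among those normal at T0. Then:

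- T1 share = p0 × s + (1 − p0) × q
- carried-over part = p0 × s ÷ T1 share

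Three assumed cases:

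- p0 = 5%, s = 30%, q = 5%: T1 share = 0.015 + 0.0475 = 0.0625; carried over 0.015 ÷ 0.0625 = 24%.
- p0 = 10%, s = 50%, q = 5%: T1 share = 0.050 + 0.045 = 0.095; carried over 0.050 ÷ 0.095 = 53%.
- p0 = 20%, s = 80%, q = 2%: T1 share = 0.160 + 0.016 = 0.176; carried over 0.160 ÷ 0.176 = 91%.

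Over p0 of 5–20%, s of 30–80% and q of 2–5%, the carried-over part runs from 24% to 91%. The range is too wide to serve as an estimate. It shows only that P36 leaves the split open.

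**Step 3: whether another planned output closes the gap.** The SAP turns change from baseline into tables for TSQM-9 (P18, P19), MSTCQ (P25), MusiQoL (P28), FSS (P31) and EDSS (P34). There is no such table for laboratory values. Neither document has a shift table or a rule for a new or worsened laboratory abnormality.

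**The case against.** A reader might infer that new abnormalities cannot be seen at all, or that the plan reports carried-over findings as effects of Peg-IFN. The documents support neither reading.

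- T0 has its own count beside T1 and T2, and no table attributes the later counts to Peg-IFN. A T1 percentage overstates nothing unless it is mistaken for an incidence.
- P37 lists every abnormality. Its columns are not specified; if they include patient and visit, individual new findings can be traced.
- The synopsis promises changes from baseline for all collected variables. Read literally, Protocol 16.3.4 also extends the repeated-measures method to the other endpoints.
- An abnormal laboratory finding can be an adverse event (Protocol 15.1.2), with onset date and relatedness assessed by the investigator and relatedness tabulated.
- This is a Phase IV patient-reported-outcome study of a registered product. Its laboratory analysis is descriptive and the primary conclusion does not depend on it.

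These points limit the claim but do not remove it. Two marginal percentages do not give within-patient transitions. P37 is a listing of abnormal values only, so a patient without a T0 entry may have been normal or not tested. A mean change does not say how many patients left the normal range. The SAP's secondary-endpoint analysis omits laboratory values. The adverse-event route relies on judgment about which findings to report; Protocol 15.2.2 gives two different starting points for recording, and the Schedule of Events marks no adverse-event collection at T0.

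**Conclusion.** The point holds as one about the planned summaries: none separates laboratory abnormalities that are new or worse since T0 from those already present under, or shortly after, the previous interferon. For a named secondary safety endpoint this is worth correcting. It does not bear on the primary analysis.

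Its size cannot be fixed from the documents. The illustration of 0 to about 28 new abnormalities assumes 10% abnormal at both visits and all 275 patients tested twice. That T0 reflects interferon exposure is an inference from the entry criterion, the two-week window and the absence of a stated washout; a short gap before the first dose is possible.

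A further tempting reading is that better tables would show whether Peg-IFN caused an abnormality. They would not. With a single arm, within-patient tables show change since the previous interferon, mixed with ordinary fluctuation around the limits of normal.

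**What to change.** Amend Protocol 16.4.2, SAP 12.b and P36 as follows.

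1. For each test, add a within-patient shift table: low, normal or high at T0 against T1, T2 or early termination, and the worst on-treatment value.
2. Report the number of patients with a new abnormality, with patients normal at T0 and retested as the denominator. Count patients, not abnormal values.
3. For patients abnormal at T0, report separately those who worsened, persisted or resolved. Define worsening in advance, for example by multiples of the normal limit or by change from T0; otherwise a marked rise from a mildly abnormal T0 value would pass as persistence.
4. Show patients with no T0 value, or with no later value, in their own rows.
5. Carry the synopsis's change from baseline into the laboratory section, and specify patient, visit and T0 value as columns of P37.
6. Reconcile Protocol 4.2 with 14.2, and the matching SAP text, on whether the tests are scheduled or discretionary.
7. Describe the results as change since the previous interferon, not as an effect caused by Peg-IFN.

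The cost is SAP wording and one extra table per test. No samples beyond those marked in the Schedule of Events are needed. The drawback is a denominator limited to patients with paired values; if testing is discretionary in practice, that may be a selected subset, and the report should say so.
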